5.6.2. Treatment Exposure and Observation Period

The duration of treatment exposure during the study in days is calculated as:

$$\text{(Date of last study drug injection - date of first study drug injection)} + x \text{ days}$$
, where x days are 7, 14, 28, 56 days for QW, Q2W, Q4W, and Q8W, respectively.

The calculations are regardless of temporary dosing interruption. The duration of exposure during the study will be summarized by treatment group using number of patients, means, SD, minimums, Q1, medians, Q3 and maximums.

In addition, the duration of exposure will be summarized categorically by counts and percentages for each of the following categories and cumulatively by these categories as well: ≥ 15 days, ≥ 29 days, ≥ 43 days, ≥ 57 days, ≥ 71 days, ≥ 85 days, ≥ 99 days, and ≥ 113 days.

The duration of observation period during the study in days is calculated as:

$$\text{(Date of the last visit - date of the first study drug injection)} + 1.$$

The number (%) of patients with observation periods will be presented by specific time periods. The time periods of interest are specified as: < 15 days, ≥ 15 days, ≥ 29 days, ≥43 days, ≥ 57 days, ≥ 71 days, ≥ 85 days, ≥99 days, ≥113 days, ≥141 days, ≥169 days, ≥197 days, ≥225 days and ≥253 days. Since the Sponsor stopped the study, it is possible that no patient reaches some time categories. If so, these categories will not be reported.

5.7. Analyses of Efficacy Variables

All efficacy variables will be summarized by descriptive statistics by treatment groups and visits during the treatment period.

The analyses of efficacy variables are described in subsections below and summarized in Section [10.1](#).

Since the Sponsor stopped the study prematurely, many patients did not reach week 16 when the study was terminated. The last assessments of such patients will be re-mapped to the next scheduled visits in general. Details have been documented in Section 6.4.

5.7.1. Analysis of Primary Efficacy Variable

The primary efficacy variable, the percent change in EASI score from baseline to week 16, will be summarized by treatment groups and visits using descriptive statistics. The results will be tabulated based on the following cases.

1. Observed values regardless of rescue treatment use
2. Observed values and the data will be censored after the rescue treatment is used

The primary efficacy data, regardless of whether the patient remains on study treatment or discontinues the study treatment but remains in the study, will be used for analysis. Specifically, if a patient stays in the study until the end of the study planned placebo-controlled treatment period, all efficacy data collected up to the study planned end of treatment visit will be included in the primary analysis, regardless of whether the patient is on treatment or not.

5.7.2. Analysis of Secondary Efficacy Variables

All secondary endpoints will be evaluated on the FAS.

The binary secondary efficacy endpoints will be analyzed using descriptive statistics by treatment groups and visits. The results will be tabulated based on the following cases.

1. Observed values regardless of rescue treatment use.
2. Observed values and the data will be censored after the rescue treatment is used. Patients with missing value due to rescue treatment will be counted as non-responder .

The continuous secondary efficacy variables will be analyzed using the same approach as that used for the analysis of the primary endpoint.

Similar to the primary endpoint, the secondary efficacy data, regardless of whether the patient remains on study treatment or discontinues the study treatment but remains in the study, will be used for analysis.

5.7.3. Adjustment for Multiple Comparison

There will be no control for multiplicity for this study.

5.8. Analysis of Safety Data

The analysis of safety and tolerability will be performed on the SAF and presented for each treatment group.

The safety analysis will be based on the reported AEs and other safety information (clinical laboratory evaluations, vital signs and 12-lead ECG).

Thresholds for Potential Clinically Significant Values (PCSV) in laboratory variables, vital signs and ECG are defined in Section 10.3.

The summary of safety results will be presented for each treatment group.

Descriptive statistics or listings will be provided for the safety endpoints for the patients impacted by COVID-19 pandemic as well as for three periods (pre-, during-, post-COVID-19 periods), if applicable.

5.8.1. Adverse Events

Listing of TEAEs, serious TEAEs, and TEAEs resulting in death and study drug discontinuation will be generated.

Numbers and proportions of patients reporting TEAEs will be summarized for treatment period and follow-up period, sorted by alphabetical order of SOC and decreasing frequency of PT based on the incidence in the REGN3500 treatment group.

Summaries of TEAEs will include:

- TEAEs
 - TEAEs by SOC/PT
 - TEAEs by SOC/HLT/PT
 - TEAEs by PT
 - Common TEAEs by SOC/PT (incidence with PT $\geq 5\%$)
 - TEAEs related to study drug as assessed by the investigator by SOC/PT
 - TEAEs related to study procedure as assessed by the investigator by SOC/PT
 - TEAEs by severity by SOC/PT
 - Severe TEAEs by SOC/PT
 - Severe TEAEs related to study drug as assessed by the investigator by SOC/PT
 - Severe TEAEs related to study procedure as assessed by the investigator by SOC/PT
 - Common non-serious TEAEs by SOC/PT (incidence with PT $\geq 5\%$)
 - TEAE per 100 patient years by SOC/PT during treatment period only
- Serious TEAEs by SOC/PT
 - Serious TEAEs by SOC/PT
 - Serious TEAEs by SOC/HLT/PT
 - Serious TEAEs related to study drug as assessed by the investigator by SOC/PT
 - Serious TEAEs related to study drug as assessed by the investigator by SOC/PT
- TEAEs leading to permanent discontinuation from study treatment by SOC/PT
- Serious TEAE per 100 patient years by SOC/PT during treatment period only
- Death by SOC/PT

- Skin infection TEAEs by SOC and PT

5.8.2. Analysis of Adverse Events of Special Interest

The adverse events of special interest (AESI) will be summarized by AESI category (see Section 10.4) and by high level term and PT.

5.8.3. Analysis of Clinical Laboratory Measurements

Laboratory measurements include clinical chemistry, hematology and urinalysis results, and will be converted to standard international units and US conventional units. Summaries of laboratory variables for overall study period, treatment period and follow-up period will include:

- Descriptive statistics of laboratory result and change from baseline by visit
- Descriptive statistics of blood eosinophils and change and percent change from baseline by visit
- The number (n) and percentage (%) of patients with treatment-emergent PCSVs
- The number (n) and percentage (%) of patients with treatment-emergent PCSVs for patients without PCSVs in corresponding category at baseline
- Shift tables based on baseline normal/abnormal and other tabular and graphical methods may be used to present the results for parameters of interest

Listing of all laboratory parameters normal range, abnormal flag and treatment-emergent PCSV by patient and visit will be provided.

5.8.4. Analysis of Vital Signs

Summaries of vital sign variables for the overall study period, treatment period and follow-up period will include:

- Descriptive statistics of vital sign variable and change from baseline by visit
- The number (n) and percentage (%) of patients with treatment-emergent PCSV
- The number (n) and percentage (%) of patients with treatment-emergent PCSVs for patients without PCSVs in corresponding category at baseline
- Shift tables based on baseline normal/abnormal and other tabular and graphical methods may be used to present the results for parameters of interest

Listings of vital sign will be provided with flags indicating the treatment-emergent PCSVs.

5.8.5. Analysis of 12-Lead ECG

Summaries of 12-lead ECG parameters by the overall study period, treatment group for treatment period and follow-up period will include:

- Each ECG parameter and change from baseline
- The number (n) and percentage (%) of subjects with treatment-emergent PCSV
- The number (n) and percentage (%) of patients with treatment-emergent PCSVs for patients without PCSVs at baseline in corresponding category
- ECG status (i.e. normal, abnormal) summarized by a shift table

Listings of ECG will be provided with flags indicating PCSVs.

5.8.6. Physical Exams

The number (n) and percentage (%) of patients with abnormal physical exams will be summarized at baseline, end of treatment period and end of study by treatment group.

5.8.7. Ophthalmological exams

The findings from the ophthalmological exams will be summarized and listed.

5.9. Analysis of Pharmacokinetic Data

No formal statistical analysis will be performed. Concentrations of functional REGN3500 and total IL-33 (REGN3500 target) in serum will be summarized at each time point by treatment group using descriptive statistics. The data may be combined with data from other studies, as applicable, for analysis using population methods. Any population PK analysis will be reported separately.

5.10. Analysis of Immunogenicity Data

5.10.1. Analysis of ADA Data

The immunogenicity variables described in Section 4.8 will be summarized using descriptive statistics in the ADA analysis set.

The following analysis will be provided based on AAS:

- Number (n) and percent (%) of ADA-negative patients (pre-existing immunoreactivity and ADA negative at all timepoints) in the respective ADA assay by treatment groups
- Number (n) and percent (%) of ADA positive patients (treatment-emergent and treatment-boosted responses) by treatment groups and ADA titer categories
- Number (n) and percent (%) of treatment-emergent ADA-positive patients by treatment group and ADA titer categories
 - a. Number (n) and percent (%) of persistent treatment-emergent ADA-positive patients
 - b. Number (n) and percent (%) of indeterminate treatment-emergent ADA-positive patients

- c. Number (n) and percent (%) of transient treatment-emergent ADA-positive patients
- Number (n) and percent (%) of treatment-boosted ADA-positive patients by treatment groups and ADA titer categories
- Listing of all ADA titer levels will be provided for patients with pre-existing, treatment-emergent and treatment-boosted ADA responses

5.11. Association of Immunogenicity with Exposure & Safety

5.11.1. Immunogenicity and Exposure

Potential association between ADA variables and systemic exposure to study treatment (REGN3500) will be explored by treatment group. Plots of study drug concentration may be provided for analyzing the potential impact of ADA response status and titer on corresponding drug concentration.

5.11.2. Immunogenicity and Safety

Association between ADA and safety event may be explored with a primary focus on the following events during the TEAE period:

- Injection site reaction (serious or severe and lasting 24 hours or longer)
- Hypersensitivity (SMQ: Hypersensitivity [Narrow])
- Anaphylaxis (SMQ: Anaphylaxis [Narrow])

The above mentioned safety analyses will be conducted using the following ADA response categories:

- ADA positive patients, that is patients with treatment-emergent or treatment-boosted response,
- ADA negative patients, that is patients with pre-existing immunoreactivity or negative in the ADA assay at all time points
- Patients with persistent treatment-emergent ADA response
- Maximum post-baseline titer level in treatment emergent or treatment boosted ADA positive patients:
 - Low (titer < 1,000)
 - Moderate ($1,000 \leq \text{titer} \leq 10,000$)
 - High (titer > 10,000)

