4.6.2. Adverse Events of Special Interest

In this study, the adverse event of special interest (AESI) category includes:

- Anaphylactic reactions or acute allergic reactions that require immediate treatment
- Severe ISRs that last longer than 24 hours
- Mycosis fungoides or other forms of cutaneous T-cell lymphoma
- Any severe infection; any infection requiring treatment with parenteral antibiotics/anti-viral/anti-fungal agent; any infection requiring treatment with oral antibiotic/anti-viral/anti-fungal for longer than 2 weeks; any clinical endoparasitosis; any opportunistic infection
- Conjunctivitis (any type or etiology), keratitis, or blepharitis (only events that are either severe or serious or lasting ≥ 4 weeks will be reported as AESIs)

- Significant ALT elevation
 - a. ALT >3×ULN associated with total bilirubin >2×ULN; or
 - b. ALT >5×ULN in patients with baseline ALT ≤2×ULN; or
 - c. ALT >8×ULN if baseline ALT >2×ULN

The search criteria for AESIs are provided in Section 10.4.

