10.4. Search Criteria for TEAE of Special Interest

The search criteria are meant to assist the process of identification of TEAE of Special Interest. However, since these criteria might not be exhaustive in some cases or may not be specific in other cases. Hence an additional blinded review of all PTs in the database may be performed by the Medical monitor, based on medical judgement, to identify any TEAE of Special Interest/TEAE Syndrome that might have been missed by the criteria or to identify any TEAE that may have been inaccurately assigned as AESI by the algorithmic search.

AESI	Search Criteria
Anaphylactic reactions	
For SMQ “anaphylactic reaction” An algorithmic approach will be used. A case must include either:
 
 1. A narrow term (a term from Category A); 2. Patient with both a term from Category B AND a term from Category C; 3. Patient with a term from Category D AND { a term from Category B - OR a term from Category C } 
For bullets 2 and 3, the search terms that are included under the SMQ for a particular event need to have the same start date (for e.g. if search shows cough (category B term) occurring at day 3 and urticaria (category C term) occurring at day 7, this event is not adjudicated as anaphylactic reaction as this is inconsistent with the clinical presentation of anaphylaxis as an acute event with simultaneous involvement of 2 or more body systems.
 
Note: manual adjudication of relevant PTs will be required by the study medical monitor, before database lock

Conjunctivitis (any type or etiology), keratitis, or blepharitis (only events that are either severe or serious or lasting ≥ 4 weeks will be reported as AESIs)	
broad CMQ conjunctivitis (Conjunctivitis, Conjunctivitis allergic, Conjunctivitis bacterial, Conjunctivitis viral, Atopic keratoconjunctivitis, Blepharitis, Dry eye, Eye irritation, Eye pruritus, Lacrimation increased, Eye discharge, Foreign body sensation in eyes, Photophobia, Ocular hyperaemia, Conjunctival hyperaemia, Xerophthalmia)
 
Blepharitis PTs (Blepharitis, blepharitis allergic)
 
AND
 
Serious AE= “Yes” OR Severity= “severe” OR lasting ≥ 4 weeks

	Note: manual adjudication of relevant PTs will be required by the study medical monitor, before database lock.

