Keratitis	
Any of the following PTs:
 
 • Keratitis • Allergic keratitis • Ulcerative keratitis • Atopic keratoconjunctivitis • Herpes ophthalmic • Ophthalmic herpes simplex 
Note: manual adjudication of relevant PTs will be required by the study medical monitor, before database lock.

Severe ISRs that last longer than 24 hours	
- HLT = Injection site reactions
 
- Severity = “severe” or Serious AE =”Yes”
 
- AE duration ≥1 day

Mycosis fungoides or other forms of cutaneous T-cell lymphoma	
-HLT = Mycoses fungoides
 
-OR LLT = Sezary syndrome
 
-OR LLT = Cutaneous T-cell lymphoma
 
-OR PT = Cutaneous T-cell dyscrasia

Any severe infection	
-SOC = Infections and infestations
 
-Severity = “severe” OR Serious AE= “Yes”

Any infection requiring treatment with parenteral antibiotics	
SOC = Infections and infestations
 
- Action taken for AE = “medication”

	- ConMed: ATC3= “Antiinfectives” during the TEAE course (between start and stop dates), Route = IV, IM
Any infection requiring treatment with oral antibiotic/anti-viral/anti-fungal for longer than 2 weeks	-SOC = Infections and infestations -Action taken for AE = “medication” -Check CM: ATC3=” BETA-LACTAM ANTIBACTERIALS, PENICILLINS” OR “OTHER ANTIBACTERIALS” during the TEAE course (between start and stop dates), Route = PO and Treatment duration >14 days
Any clinical endoparasitosis	-HLT = Cestode infections -HLT = Helminthic infections NEC -HLT = Nematode infections -HLT = Trematode infections
Any opportunistic infection ^a a: The definition of opportunistic infections is referring to the recent consensus guidance for opportunistic infections in the setting of biologic therapy (K L Winthrop et al, 2015)	The following HLTs plus PTs -HLT = Pneumocystis infections -HLT* = Fungal infections NEC -HLT* = Pseudallescheria infections -HLT = Herpes viral infections -HLT = Paracoccidioides infections -HLT = Sporothrix infections -HLT = Cryptosporidia infections -HLT* = Trypanosomal infections -HLT* = Campylobacter infections -HLT* = Shigella infections -HLT* = Vibrio infections Plus the following PTs -Polyomavirus-associated nephropathy -BK virus infection -Cytomegalovirus infection -Post transplant lymphoproliferative disorder -Progressive multifocal leukoencephalopathy -*Bartonellosis -Blastomycosis -Toxoplasmosis

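### SAP 5.11.2 and 10.4 identify anaphylaxis by different rules, and the injection-site-reaction rules in both are wider than the AESI definition in SAP 4.6.2

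*SAP*

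**What the plan says.** **Anaphylaxis.** For the comparison of safety events by ADA status, SAP 5.11.2 lists "Anaphylaxis (SMQ: Anaphylaxis [Narrow" and a separate hypersensitivity row, also narrow. It mentions no algorithm or adjudication and does not refer to SAP 10.4. The AESI search in SAP 10.4 has three routes. The first is "A narrow term (a term from Category A". The second is "Patient with both a term from Category B AND a term from Category C". The third is a Category D term with a term from B or C. Routes 2 and 3 need a common start date. The row then states that "manual adjudication of relevant PTs will be required by the study medical monitor, before database lock".

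**Injection-site reactions.** SAP 4.6.2 defines the AESI as "Severe ISRs that last longer than 24 hours", and protocol 9.4.3 has the same definition. SAP 5.11.2 uses "Injection site reaction (serious or severe and lasting 24 hours or longer". The search in SAP 10.4 takes the injection-site-reaction HLT, severity severe or seriousness yes, and "AE duration ≥1 day".

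**How they connect.** SAP 5.8.2 builds the AESI summary on the categories of Section 10.4. The incidence of treatment-emergent AESIs is a secondary safety endpoint (protocol 4.2.2). The opening text of SAP 10.4 allows, but does not require, a blinded review to add missed events or remove wrongly assigned ones. The ISR row has no adjudication note of its own.

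**The concern.** Anaphylaxis and severe injection-site reactions are natural events to relate to anti-drug antibodies for an injected antibody. If two sections of one SAP select them by different rules, a patient can be an anaphylaxis case in the AESI table and not in the anaphylaxis row by ADA status. A reader of the report could not tell whether the difference is a finding or an artefact of the search.

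For ISRs, the rule that will be programmed is the 10.4 search. If that search is wider than the definition in 4.6.2 and the protocol, the AESI count can include events that the definition excludes. Safety and immunogenicity are also what this stopped trial carries forward, because SAP 1.1 says that development in other diseases continues.

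**Working it through.** The plan gives no figure to reproduce on this point, so the check applies each rule to the possible cases.

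**1. Anaphylaxis.** The inputs are the three routes in SAP 10.4, with terms assumed to share a start date, and the narrow-only rule in SAP 5.11.2. SAP 10.4 itself equates a narrow term with Category A.

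- 10.4 candidate: A, or (B and C), or (D and (B or C)).
- 5.11.2 event: A.
- Patterns of presence or absence of A, B, C and D: 2^4 = 16.
- Patterns that qualify under 10.4 but not 5.11.2: B+C, B+D, C+D and B+C+D, each without A, so 4 of 16.
- Patterns that qualify under 5.11.2 but not 10.4, before adjudication: 0.

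The 4 of 16 counts logical patterns. It is not an expected share of cases.

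**2. ISR rules side by side.** The 5.11.2 column reads the duration as applying to both serious and severe reactions.

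| ISR | 4.6.2 and protocol 9.4.3 | 5.11.2 | 10.4, elapsed hours | 10.4, end date − start date + 1 |
|---|---|---|---|---|
| Severe, not serious, 12 h | no | no | no | yes |
| Severe, not serious, 24 h | no | yes | yes | yes |
| Severe, not serious, 36 h | yes | yes | yes | yes |
| Serious, not severe, 12 h | no | no* | no | yes |
| Serious, not severe, 24 h | no | yes | yes | yes |
| Serious, not severe, 36 h | no | yes | yes | yes |

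*Yes, if the duration condition in 5.11.2 is read as attaching only to severe reactions; the wording allows both readings.

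Two differences do not depend on how duration is computed: the serious non-severe ISR, and the severe ISR of exactly 24 hours.

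**3. ISRs shorter than 24 hours.** The SAP gives no formula for AE duration.

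- End date − start date + 1, the day count that SAP 5.6.2 uses for the observation period: every event has a duration of at least 1, so the filter removes nobody.
- End date − start date: a 12-hour ISR passes if it crosses midnight, so if onset is at 12:00 or later. With onset uniform over the day (assumption) this is 12/24 = 50%. With onset uniform from 09:00 to 17:00 (assumption) it is 5/8 = 63%.
- Elapsed hours of at least 24: no ISR shorter than 24 hours passes.

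On each convention, an ISR that meets 4.6.2 and has complete dates also passes the 10.4 search, so the error is over-inclusion. An ongoing ISR, or one without a stop date, has no stated duration, because SAP 6.3 imputes AE end dates only as an intermediate step for start dates.

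**4. Size of one misclassification.** SAP 2.2 gives 129 randomized patients in 5 arms: 129/5 = 25.8, about 26 per arm. One patient is 1/26 = 3.8 percentage points. Actual arm sizes are not given, and the share is larger if the analysis set is smaller.

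**The case against.** The strongest reply is that Section 10.4 is a search aid, not a rival definition. It says so itself and allows a blinded correction, while 4.6.2 remains the definition and is repeated as the label of the ISR row. This has weight, and it means one cannot say that the AESI incidence will depart from its definition. But the correction is optional, and the ISR row lacks the required adjudication that the anaphylaxis, conjunctivitis and keratitis rows have.

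Some stronger conclusions are tempting but not supported:

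- *That cases found through B+C or D drop out of the ADA exploration altogether.* Only absence from the anaphylaxis row is shown. The hypersensitivity row may catch them; the documents do not list its terms.
- *That a narrow-term event rejected at adjudication would still count in 5.11.2.* This assumes that 5.11.2 uses unadjudicated events, which the SAP does not say.
- *That the AESI table and the ADA exploration will give different ISR counts.* Read naturally, 5.11.2 and 10.4 are nearly the same ISR rule. They part only if a day means a calendar date.
- *That ISRs of a few hours will be counted.* This needs a calendar-day convention. SAP 6.1 uses AE time to set baseline, so an hours-based duration is possible.

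The route through seriousness is also narrow. Protocol 9.5.1 already grades an ISR as severe if it needs an emergency room visit or hospitalization, so few serious ISRs would be non-severe. Finally, narrow terms could be a deliberate choice for an exploration. If so, the SAP should say it, because a reader will expect the two anaphylaxis counts to agree.

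**Conclusion.** The mismatch is in the text, and its impact is modest. An adjudicated anaphylaxis AESI can be missing from the anaphylaxis row of the ADA-safety exploration. The ISR rules in 5.11.2 and 10.4 admit a serious non-severe reaction and one of exactly 24 hours, both outside the definition in SAP 4.6.2 and protocol 9.4.3. Admission of ISRs shorter than 24 hours is conditional on a calendar-day count, which the SAP neither adopts nor excludes.

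One affected patient moves an arm's rate by about 4 percentage points, assuming about 26 patients per arm. The documents give no expected frequency for these events, so the number of affected patients cannot be estimated. No inference is at risk: SAP 1.1 makes all analyses descriptive, the 5.11.2 exploration is optional, and only an abbreviated report is planned (SAP 1.2.4). The reason to act is that a secondary safety endpoint depends on a search rule that can misclassify events and is cheap to correct.

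**What to change.** Before database lock:

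1. In SAP 5.11.2, replace the narrow-SMQ anaphylaxis entry with the anaphylaxis events identified and adjudicated under Section 10.4.
2. In the ISR row of SAP 10.4 and the ISR entry of 5.11.2, use the 4.6.2 definition: severe and longer than 24 hours. State the formula: stop date/time minus start date/time, greater than 24 hours, where both times are recorded.
3. Add to the ISR row a required blinded adjudication before database lock for severe ISRs with missing times or ongoing status. This is needed because the documents do not show that AE stop times are collected, and the row has no required adjudication now.

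Serious non-severe ISRs would leave the ISR row of the ADA exploration and the ISR AESI count, but they remain in the serious TEAE tables of SAP 5.8.1. The cost is a few lines of SAP text, a small programming change and a few more events for the medical monitor to adjudicate.
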